Study Design	
 This is a phase IIIB, 24-week, randomised, double-blind, parallel group, multicenter study evaluating FF/UMEC/VI (100/62.5/25mcg) delivered via a single ELLIPTA ('closed' triple) plus matching placebo ELLIPTA versus FF/VI (100/25mcg) + UMEC (62.5mcg) delivered via two ELLIPTAs ('open' triple), all taken once daily. Subjects will be randomized 1:1 to either FF/UMEC/VI or FF/VI+UMEC. The randomisation will be stratified based on long-acting bronchodilator usage during the run-in (none, one or two long-acting bronchodilators per day). A study with 816 evaluable subjects for the primary analysis will have 90% power to determine non-inferiority of FF/UMEC/VI to FF/VI+UMEC based on trough FEV1 at Week 24, an estimate of residual standard deviation (SD) for trough FEV1 at Week 24 of 220mL, at the one-sided 2.5% significance level when the margin of non-inferiority is 50mL and the true mean treatment difference is assumed to be 0mL. Based on approximately 20% of subjects who are randomized discontinuing study treatment or being excluded from the mPP population at Week 24, approximately 1020 subjects will be randomised
Planned Analyses	
 No interim analyses are planned for this study.

Overview	Key Elements of the RAP
	
 All decisions regarding final analysis, as defined in this RAP document, will be made by Source Data Lock (SDL) prior to Study Data Tabulation Model (SDTM) Database Freeze (DBF) of the study data except for the identification of protocol deviation (PD) that require treatment details. The PD of taking incorrect treatment and treatment non-compliance (based on active treatment) will be identified following DBF.

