<pre>proc mixed data=<dataset>; class treatment visit cengroup stratum subjid; model endpoint=baseline stratum visit cengroup treatment visit*baseline visit*treatment / ddfm=kr; repeated visit/ subject=subjid type=un; lsmeans visit*treatment / cl diff e om=OMdset at (baseline)=(&blm.); ods output lsmeans=lsmeans; ods output diffs=diffs; run;</pre> 
where OMdset is a dataset with a row for every subject-visit combination that contains all of the covariates and blm is a macro variable containing the mean baseline for the subjects used in the analysis. This is used to derive the LS means using coefficients which are based on the subjects used in the analysis.

Sensitivity and Supportive Statistical Analyses

 ○ The above will be repeated for the ITT population. LS mean and LS mean change from

Sensitivity and Supportive Statistical Analyses

baseline with their corresponding SEs will be presented for each treatment by Visit, together with estimated treatment differences and the corresponding 95% CIs.

- A “tipping point” sensitivity analysis of trough FEV1 at Week 24 will be conducted for the mPP Population. This will explore the impact of missing data by using differing assumptions regarding the mean treatment effect in subjects who discontinue study treatment or have data excluded from the mPP Population analyses. Mean treatment effects investigated will range from a change from baseline of -150mL to +150mL in increments of 50mL. For each value of the assumed mean change from baseline on FF/UMEC/VI, the full range of values for the assumed mean change from baseline for FF/VI+UMEC will be investigated; thus including scenarios where subjects who discontinue FF/UMEC/VI have a lower treatment effect than those who discontinue FF/VI+UMEC and vice versa. The analysis results will be used to explore the conditions under which the conclusion of non-inferiority no longer holds.

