- For each subject with missing or excluded data at Week 24, a value will be imputed based on a random draw from a normal distribution with mean equal to the corresponding assumed mean change from baseline and standard deviation taken from the observed change from baseline data for the combined treatment arms at the Week 24 visit. Data for subjects with missing baseline values will not be imputed. Analysis of the complete Week 24 dataset will be carried out using an ANCOVA model with covariates of treatment group, stratum (number of long-acting bronchodilators per day during the run-in), geographical region and baseline.
- The seed will be set using the following SAS code:

```

data seed1;
  number=round(10000*ranuni(0),1);
  output;
run;

proc print;
run;

```

The seeds generated and assigned to each analysis will be documented separately prior to DBF.

A table will be produced displaying the 95% CI for the treatment difference at Week 24 under the above assumptions for the mean changes from baseline for each of the treatment arms.
- Interactions between treatment and other factors will be investigated as follows by adding interaction terms to the specified model:
 - An assessment of whether the effect of treatment on trough FEV1 is modified by number of long-acting bronchodilators per day during the run-in, geographic region, or baseline will be made by fitting separate repeated measures models, identical to the primary analysis models described above but also including additional terms as described below.
 - For the factors of number of long-acting bronchodilators per day during the run-in and

Sensitivity and Supportive Statistical Analyses	

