10.7.2. Handling of Missing Data

Element	Reporting Detail
General	
 Missing data occurs when any requested data is not provided, leading to blank fields on the collection instrument : 
 These data will be indicated by the use of a “blank” in subject listing displays. Unless all data for a specific visit are missing in which case the data is excluded from the table. Answers such as “Not applicable” and “Not evaluable” are not considered to be missing data and should be displayed as such. No imputation will be made for any missing numerical data, except in the sensitivity analysis of the primary endpoint to assess the impact of missing data on study results. Missing data will generally not be considered in the calculation of percentages (i.e., the denominator will not include subjects who have missing data at a given time point).
Responder	
 Subjects with a missing baseline will have responder status as missing. Subjects with missing post-baseline data and a subsequent non-missing assessment will not be considered a responder or non-responder but will be left as missing. Subjects with a baseline but all missing post-baseline data will be considered a non-responder at all time points.

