10.13.5. Efficacy Tables

Efficacy: Tables			
No.	Populatio n	Title	Deliverable
Spirometry			
2.1	ITT	Summary of Baseline FEV1 (L)	SAC
2.2	MPP	Summary of Baseline FEV1 (L)	SAC
2.3.	ITT	Summary of Baseline FEV1 (L) by Country	SAC
2.4.	ITT	Summary of Trough FEV1 (L)	SAC
2.5.	MPP	Summary of Trough FEV1 (L)	SAC
2.6.	ITT	Summary of Trough FEV1 (L) by Country	SAC
2.7.	ITT	Analysis of Trough FEV1 (L)	SAC
2.8.	MPP	Analysis of Trough FEV1 (L)	SAC
2.9.	ITT	Significance Levels for Interactions of Treatment with Number of Long-acting Bronchodilators per Day During the Run-in, Geographical Region, and Baseline for Analysis of Trough FEV1 (L)	SAC
2.10.	mPP	Significance Levels for Interactions of Treatment with Number of Long-acting Bronchodilators per Day During the Run-in, Geographical Region, and Baseline for Analysis of Trough FEV1 (L)	SAC

Efficacy: Tables			
No.	Population	Title	Deliverable
2.11.	MPP	Trough FEV1 (L) Tipping Point Sensitivity Analysis: 95% CIs after Imputing Varying Week 24 Mean Change from Baseline Trough FEV1 (L)	SAC
2.12.	ITT	Summary of Baseline FVC (L)	SAC
2.13.	ITT	Summary of Trough FVC (L)	SAC
SGRQ			
2.14.	ITT	Summary of Baseline SGRQ Scores	SAC
2.15.	ITT	Summary of SGRQ Scores	SAC
2.16.	ITT	Analysis of SGRQ Total Score	SAC
2.17.	ITT	Summary and Analysis of Proportion of Responders According to SGRQ Total Score	SAC
COPD Exacerbations			
2.18.	ITT	Summary of On-Treatment COPD Exacerbations	SAC
2.19.	ITT	Summary of Post-Treatment COPD Exacerbations	SAC
2.20.	ITT	Summary and Analysis of Time to First On-treatment Moderate or Severe Exacerbation (days)	SAC
SACBDI/TDI			
2.21.	ITT	Summary of SAC BDI Focal Score	SAC
2.22.	ITT	Summary of SAC TDI Focal Score	SAC
2.23.	ITT	Analysis of SAC TDI Focal Score	SAC
2.24.	ITT	Summary and Analysis of Proportion of Responders According to SAC TDI Focal Score	SAC

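### The tipping-point analysis is specified with one random draw per missing Week 24 value and no repetition or pooling, so verdicts next to the tipping boundary depend partly on the seed

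*SAP*

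**What the plan says.** SAP 7.1.2 (Sensitivity and Supportive Statistical Analyses) sets up a grid of assumed mean changes for the subjects whose Week 24 value is missing or excluded: "Mean treatment effects investigated will range from a change from baseline of -150mL to +150mL in increments of 50mL". All pairs across the two arms are run, which makes 7 x 7 = 49 cells. In each cell "a value will be imputed based on a random draw from a normal distribution with mean equal to the corresponding assumed mean change from baseline", with the SD taken from the observed Week 24 changes in both arms combined. Then "Analysis of the complete Week 24 dataset will be carried out using an ANCOVA model", and a table shows the 95% CI for each pair of assumed means. The purpose is stated: "The analysis results will be used to explore the conditions under which the conclusion of non-inferiority no longer holds".

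On seeds, the SAP gives code to generate them and adds: "The seeds generated and assigned to each analysis will be documented separately prior to DBF". It does not say whether each cell has its own seed or one seed serves the whole grid.

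The other relevant places add nothing on repetition. SAP 10.7.2 says "No imputation will be made for any missing numerical data, except in the sensitivity analysis of the primary endpoint". SAP 10.7.2.2 only refers back to 7.1.2. The one planned output, Table 2.11, is titled "Tipping Point Sensitivity Analysis: 95% CIs after Imputing Varying Week 24 Mean Change from Baseline". Protocol 9.4.2 describes the aim but not the mechanics.

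**The concern.** The wording is singular throughout: one value, one draw, one completed dataset. A programmer following it would impute once per cell. The estimate in each cell then contains a random component that has nothing to do with the trial data and would change with another seed.

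In most of the grid this does no harm. It matters where the lower confidence limit lies near -50 mL, and locating that boundary is the purpose of the analysis.

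The primary MMRM treats all missing and excluded data as missing at random (SAP 5.1 and 7.1.2). The ITT MMRM puts back on-treatment values that were observed but excluded from the mPP analysis, so it tests that part of the assumption. It too assumes missing at random for data lost after discontinuation, and SAP 5.1 notes that no off-treatment FEV1 was collected. For those data the tipping-point table is the planned check.

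**Working it through.** **Inputs.** From Protocol 9.2.1: 1020 randomised 1:1 (510 per arm), about 20% discontinued or excluded at Week 24 (102 per arm), residual SD 220 mL, margin 50 mL, one-sided 2.5%. From Protocol Table 4: SD range 180 to 260 mL. From SAP 7.1.2: 50 mL grid steps from -150 to +150 mL. The documents do not give the SD of change from baseline, so the residual SD stands in for it. The observed difference is set to 0.

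**The plan's own figures.** With 408 per arm, power = Phi(50/(220 x sqrt(2/408)) - 1.96) = Phi(1.29) = 90%, as stated. The other four powers in Table 4 also reproduce, and 816/0.8 = 1020.

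**Noise from one draw.** Let p be the imputed share and m the number imputed per arm. Each arm mean contains p times the mean of m random draws, so

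seed SD of the difference = p x SD x sqrt(2/m) = 0.2 x 220 x sqrt(2/102) = 6.2 mL (5.0 at SD 180, 7.3 at SD 260).

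The 95% range is +/-12.1 mL (9.9 to 14.3). One grid step in one arm moves the estimate by 0.2 x 50 = 10 mL, so the seed SD is 0.62 of a step (0.50 to 0.73).

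**Effect on the verdict.** Let d be the assumed mean for FF/UMEC/VI minus that for FF/VI+UMEC. The CI half-width is 1.96 x 220 x sqrt(2/510) = 27.0 mL. The expected lower limit is 0.2d - 27.0, and the chance of a non-inferior verdict is Phi((0.2d - 27.0 + 50)/6.16).

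| d (mL) | Cells | Expected lower limit (mL) | Chance of non-inferior verdict |
|---|---|---|---|
| 0 | 7 | -27.0 | 100% |
| -50 | 6 | -37.0 | 98% |
| -100 | 5 | -47.0 | 69% |
| -150 | 4 | -57.0 | 13% |
| -200 | 3 | -67.0 | 0.3% |

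Counting a cell as seed-dependent when this chance lies between 5% and 95%, there are 5 + 4 = 9 such cells of 49.

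**Simulation.** On one fixed dataset, with ANCOVA on treatment and baseline and 10,000 redraws per cell, non-inferiority failed in 2.3%, 34%, 88% and 99.7% of draws at d = -50, -100, -150 and -200 mL. At d = -100 mL the central 95% of lower limits ran from -59.5 to -35.2 mL. In a simpler simulation with two-sample means, 1000 seeds each shared by all cells gave 34 to 43 non-inferior cells of 49 (2.5th to 97.5th percentile). With a separate seed per cell, about 30% of 500 simulated tables had verdicts out of order; with a shared seed none of 1000 did.

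**Other inputs.**
- SD 180: the same 9 cells (94% at -100 mL, 34% at -150 mL).
- SD 260: 15 cells (87% at -50, 40% at -100, 5% at -150 mL).
- 1059 subjects, the sum of the regions in SAP 10.8.1 (398 + 252 + 215 + 194): seed SD 6.0 mL.
- Half of the 20% fully excluded and so outside mPP (SAP 10.1.2), leaving 51 of 459 per arm imputed: seed SD 4.8 mL (4.0 to 5.7) against a step of 50 x 51/459 = 5.6 mL. At SD 220 the affected cells move to d = -150, -200 and -250 mL (84%, 44%, 10%), again 4 + 3 + 2 = 9.
- Observed difference other than 0 (SD 220, 20% imputed): 13 cells at -20 mL, 7 at +10 or +20, 5 at +30, 3 at +40.

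**With 100 imputations.** The seed SD of the estimate falls to 6.16/sqrt(100) = 0.62 mL. The Rubin half-width is 1.96 x sqrt(13.78^2 + 6.16^2) = 29.6 mL, where 13.78 = 220 x sqrt(2/510). At d = -100 mL the pooled lower limit is -20 - 29.6 = -49.6 mL.

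**The case against.** **The SAP never says single imputation.** True; this is read from the singular wording and the absence of a count or combining rule. A plan that meant multiple imputation would need both, so the text as written leads to one draw.

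**The count of nine cells depends on an observed difference of 0.** It does. It runs from 13 to 3 cells over observed differences of -20 to +40 mL, but it does not reach zero at any value tried.

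**Rubin's rules do more than remove noise.** This stands. The planned interval is not too narrow: the assumed means are fixed, and the single-draw standard error of 13.8 mL already matches sampling plus draw variance. Averaging the draws away leaves a sampling standard error of about 12.3 mL (sqrt(0.8) x 13.78), whereas Rubin's gives 15.1 mL. Pooling therefore shifts the boundary slightly in the conservative direction, for example from -47.0 to -49.6 mL at d = -100 mL. The defect is avoidable simulation noise, not understated uncertainty.

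**Pooling leaves the d = -100 mL cells on the edge.** At exactly the planning values the chance of a non-inferior verdict there is about 74% after pooling, against 69% before. But the limit is then steady to within about 1.5 mL instead of 12 mL, and the -50 and -150 mL cells are settled.

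**It is an exploratory table with documented seeds.** Also true, and the primary conclusion does not rest on it. Documenting a seed makes a run repeatable but does not stop the boundary from depending on it.

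**Conclusion.** The point holds. As specified, the tipping-point table has a seed SD of about 6.2 mL per cell against 10 mL between neighbouring cells, and about 9 of 49 verdicts turn materially on the seed. These figures assume 20% imputed, an SD of 220 mL for the change from baseline and an observed difference of 0; none of the three is known from the documents as an observed value. The size changes over plausible ranges, but the dependence remains.

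The effect is confined to cells near the boundary of a sensitivity analysis. The primary MMRM, the ITT MMRM and the non-inferiority decision involve no random draws. This is a change that should be made, not one on which the trial's conclusion hangs.

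**What to change.** In SAP 7.1.2, state that for each cell the imputation is repeated many times (for example 100 or more), that the ANCOVA is run on each completed dataset, and that estimates and variances are pooled by Rubin's rules. State that one seed stream serves all cells, which keeps the table in order.

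Fix the seeds by source data lock, the cut-off that SAP section 1 sets for analysis decisions. The present deadline is database freeze, and SAP 3.1 puts unblinding (step 4) before that freeze (step 6), so it does not guarantee that seeds are set blind.

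Computing each cell without random draws would also remove the noise, provided the variance formula is written down in advance.

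The cost is a few lines of SAS (a loop and PROC MIANALYZE), computing time and SAP wording. Half-widths grow from 27.0 to 29.6 mL at SD 220 (22.1 to 24.2 at SD 180, 31.9 to 35.0 at SD 260). No new data are needed and the primary analysis is unchanged.

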8. SECONDARY STATISTICAL ANALYSES

8.1. Other Efficacy Analyses

8.1.1. Overview of Planned Efficacy Analyses

The other efficacy analyses will be based on the ITT population, unless otherwise specified.

Table 4 provides an overview of the planned efficacy analyses, with further details of data displays being presented in Section 10.13, List of Data Displays.

Table 4 Overview of Planned Efficacy Analyses

	Absolute								Change from Baseline							
	Stats Analysis			Summary		Individual			Stats Analysis			Summary		Individual		
	T	F	L	T	F	F	L	T	F	L	T	F	F	L		
SGRQ																
Baseline SGRQ Scores				Y			Y									
SGRQ Domain Scores				Y			Y				Y					
SGRQ Total Score (MMRM Analysis)	Y			Y			Y	Y	Y		Y	Y ²		Y		
Proportion of Responders according to SGRQ Total Score	Y			Y			Y									
Baseline Dyspnea Index (BDI)/Transitional Dyspnea Index (TDI)																
BDI				Y			Y									
TDI	Y	Y		Y			Y									
Proportion of Responders according to TDI Focal Score	Y			Y			Y									
COPD Exacerbations																
Exacerbation Occurrence and Details				Y ¹			Y									

	Absolute							Change from Baseline						
	Stats Analysis			Summary		Individual		Stats Analysis			Summary		Individual	
	T	F	L	T	F	F	L	T	F	L	T	F	F	L
Time to First On-treatment Moderate/Severe Exacerbation	Y	Y ³		Y			Y							

NOTES :

- T = Table, F = Figure, L = Listing, Y = Yes display generated.
- Stats Analysis = Represents TFL related to any formal statistical analyses (i.e. modeling) conducted.
- Summary = Represents TFL related to any summaries (i.e. descriptive statistics) of the observed raw data.
- Individual = Represents FL related to any displays of individual subject observed raw data.
 1. Number and percent reporting COPD exacerbation and summary of details regarding the exacerbation. Repeat for post-treatment exacerbations.
 2. empirical distribution function plot
 3. Kaplan -Meier Plot

8.1.1.1. St. George’s Respiratory Questionnaire for COPD Patients (SGRQ-C)

The SGRQ-C is completed at Week 0, Week 12, and Week 24. The calculation for the SGRQ-C, including how to handle missing values, is detailed in the SGRQ-C manual (Jones, 2016). The conversion of the SGRQ-C scores to SGRQ scores is as described in the manual and as detailed in Section 10.6.4.

Subjects will be classified as responders/non-responders based on SGRQ total score as described in Section 10.6.4

8.1.1.2. COPD Exacerbations

The definition of moderate and severe exacerbations is provided in Section 10.6.4. The definition of on- and post-treatment exacerbations is provided in Section 10.4.2.

For summary of on-treatment COPD exacerbations, details of the event to be summarized include the number and percent of subjects reporting an exacerbation (any severity, mild, moderate, severe and moderate/severe), number and percent subjects with each number of moderate/severe exacerbations (0, 1, ≥2), outcome, severity, duration, whether treatment with systemic or oral steroids was required, whether treatment with antibiotics was required, whether hospitalization was required, and whether the exacerbation resulted in a visit to the emergency room. Post-treatment exacerbations will be similarly summarized. The total number of exacerbations will be included. For derivation of time to first on treatment moderate or severe exacerbation, see Section 10.6.4.

8.1.1.3. Baseline Dyspnea Index (BDI)/Transitional Dyspnea Index (TDI) Focal Score

BDI is assessed at Week 0. TDI is assessed at Week 12 and Week 24. The BDI and TDI focal scores [Mahler, 2004] will be calculated as shown in Section 10.6.4.

8.1.2. Planned Other Efficacy Statistical Analyses

8.1.2.1. SGRQ Total Score

Secondary Statistical Analyses
Endpoint(s)
○ SGRQ total score
Model Specification, Model Checking & Diagnostics, Model Results Presentation
○ Same as for trough FEV1, see Section 7.1.2
○ Visit includes week 12 and 24.

8.1.2.2. TDI

Secondary Statistical Analyses
Endpoints
● TDI focal score
Model Specification, Checking, Results Presentation and SAS code
● Same as for trough FEV1, see Section 7.1.2
● BDI will be used in place of baseline.
● Visit includes week 12 and 24.

8.1.2.3. Proportion of Responders according to SGRQ Total Score and Responders according to TDI

Endpoints
● Proportion of Responders according to SGRQ total score
● Proportion of Responders according to TDI
Model Specification
● Generalized Linear Mixed Model
● Terms in the model: Dependent Variable: Response (Yes/No) Categorical : treatment group, stratum, geographical region, visit Continuous : Baseline (for SGRQ total score) or BDI Interaction : baseline*Visit, treatment*Visit Repeated : Visit
● The model will be fit with an unstructured variance-covariance matrix
● One single model to include all visits
○ SGRQ: include Week 12 and 24
○ TDI: include Week 12 and 24
Handling of Missing Data for Analysis
● Subjects with missing on-treatment data and a subsequent non-missing on-treatment scheduled assessment will not be considered as a responder/non-responder but will be left as missing.
● Subjects that have withdrawn from the study prior to the visit in question will be imputed as

non-responders at all visits post-withdrawal where the assessment was expected to be performed.

 Refer to Appendix 11: Model Checking and Diagnostics for Statistical Analyses.
Model Results Presentation

 Number and percentage of responders and non-responders for each treatment at each Week Odds ratio for comparison between FF/UMEC/VI and FF/VI+UMEC with associated 95% CI
Example SAS Code
<pre>proc glimmix data=filename ; class treatment stratum visitnum subjid centgroup; model respond(event="1") = treatment base stratum visitnum centgrp visitnum*base visitnum*treatment / dist=binary link=logit ddfm=kr solution; lsmeans visitnum*treatment / cl diff or om ; random visitnum / subject=subjid residual type=un; ods output diffs=differs; run;</pre>

8.1.2.4. COPD Exacerbations

Secondary Statistical Analyses
Endpoints

 Time to first on-treatment moderate/severe COPD exacerbation
Model Specification

 Cox's proportional hazards model 
Terms in the model:
 
Dependent variable: time to first on-treatment moderate/severe exacerbation
 
Categorical: treatment group, gender, exacerbation history (0, 1, >=2 moderate/severe exacerbations in the last 12 month at screening), smoking status (screening), stratum and geographical region.
 
Continuous: % predicted FEV1 at Baseline
 
 Use the 'exact' method for handling ties. (If the analysis will not run using the 'exact' method, then the 'Efron' method for handling ties will be used instead.)
Handling of Missing Data for Analysis

 Subjects who withdrew from the study prior to experiencing a COPD exacerbation will be considered censored at random.
Model Checking & Diagnostics

 Refer to Appendix 11: Model Checking and Diagnostics for Statistical Analyses.
Model Results Presentation

 Hazard ratio for comparison between FF/UMEC/VI and FF/VI+UMEC with associated 95% CI
Example SAS Code

Secondary Statistical Analyses
proc phreg data=<dataset> ; model timeto1*eventflag(0)=treatment fevpred stratum cengroup smokehis hxf_exac / risklimits ties=exact; run;

Secondary Statistical Analyses
Endpoints

 • Time to first on-treatment moderate/severe COPD exacerbation
Model Specification

 ○ A Kaplan-Meier analysis will also be performed for figure showing Kaplan-Meier survivor functions of the proportion of subjects with a first exacerbation over time for each treatment group separately plotted on the same figure.
Example SAS code
proc lifetest data=destin outsurv=survest; time timeto1*eventflag(0); strata treatment; run;
Model Results Presentation

 ○ Probability of having an event, 95% CI and first quartile time to exacerbation (estimate of the time at which 25% of subjects in each treatment group would have had an exacerbation) ○ Figure showing Kaplan-Meier survivor functions of the proportion of subjects with a first exacerbation over time for each treatment group separately plotted on the same figure.

